1.0 Study Summary

Table of Study Summary:

Study Title	Early Feasibility Prospective Open-Label Study to Assess the Function of a Novel Pessary for the Non-Surgical Management of Pelvic Organ Prolapse			
Study Design	Farly feasibility study of a medical device			
Primary Objective	 To assess the ability of the study device to be retained during Valsalva compared to the ability of the subject's current pessary to be retained during Valsalva (by measuring the distance from each pessary's leading edge to the hymen) To assess the ability of the study device to be retained throughout regular activity (by vaginal examination) 			
Secondary Objective(s)	 To assess the shape of the study pessary during expulsion if it is not able to be retained (by vaginal examination) To assess the orientation of the study pessary stem following regular activity (by vaginal examination) To assess the discomfort experienced with removal of the subject's current pessary compared to the discomfort experienced with removal of the study pessary (by visual analog scale) To assess the discomfort experienced with insertion of the subject's current pessary compared to the discomfort experienced with insertion of the study pessary (by visual analog scale) To globally assess the comfort associated with use of the study pessary (by visual analog scale) 			
Research Intervention(s)/ Investigational Agent(s)	Temporary placement and assessment of a novel vaginal pessary			
IND/IDE #	Device to be considered for an abbreviated IDE (non-significant risk device)			
Study Population	Current users of a ring style or Gellhorn pessary for treatment with Stage II or greater pelvic organ prolapse			
Sample Size	15-20			
Study Duration for individual participants	One hour			
Study Specific Abbreviations/ Definitions	HRT – Hormone Replacement Therapy POP – Pelvic Organ Prolapse POP-Q – Pelvic Organ Prolapse Quantification UI – Urinary Incontinence VAS – Visual Analogue Scale FPMRS – Female Pelvic Medicine and Reconstructive Surgery			

PROTOCOL TITLE: *Early Feasibility Prospective Open Label Study to Assess the Function of a Novel Pessary for the Non-Surgical Management of Pelvic Organ Prolapse*

2.0 Objectives

This is an early feasibility, open-label, non-randomized trial to obtain preliminary information about the function and effectiveness of a novel vaginal pessary for the use in women who suffer from symptoms of pelvic organ prolapse (POP). Recruited subjects will have Stage II POP or greater and will be current users of a legally marketed vaginal pessary. In a single visit, data will be collected on the performance and comfort of the subject's current pessary. After fitting and placement of a study pessary, comparative data will be collected between subject's current pessary and the study pessary on ability to support prolapse. The study pessary's function will be assessed under controlled circumstances. The subject will have her current pessary replaced at the conclusion of the visit. Results will be used to inform future design modifications of the study pessary.

3.0 Background

POP is a prevalent condition that can be observed in over 50% of women over the age of 50.¹ POP results from a weakening of the pelvic floor connective tissue and muscles, allowing the uterus or vaginal walls to descend. Typical symptoms, which include bulge and pressure, urinary dysfunction, defecatory dysfunction, and sexual dysfunction, can result in physical discomfort, emotional distress, and disrupt activities of daily life. Using published data on weighted prevalence rates of specific pelvic floor disorders² in conjunction with US census data, it can be estimated that the number of US women with symptomatic prolapse in 2016 was 3.6 million. The lifetime risk for a woman to have surgery for pelvic organ prolapse is 12.6%, or 1:8.³ As the specialty of Female Pelvic Medicine and Reconstructive Surgery (FPMRS) matures and surgical outcomes are being followed with more scrutiny, it is becoming increasingly clear that surgical treatment options are less effective than once believed. The 3 most effective and commonly performed procedures for apical prolapse have estimated composite recurrence rates by 6 years of 43%, 49%, and 57%.⁴

The vaginal pessary is an effective treatment option which is inserted in the vagina and acts as a shelf resting upon the pelvic floor muscles to support the descending organs. Often, it is as effective to abate the burdens of prolapse as a successful reconstructive surgery. 77% of practicing urogynecologists recommend a vaginal pessary as the first line treatment option for their patients with POP.⁵ Based on this number, statistics cited above, and financial information from current pessary makers, there are ~2.3 million women in the United States who use a pessary for POP. A pessary is not surgically implanted and can be removed and reinserted but is only effective while in situ. The root cause failure of current pessaries in common use is their rigid and fixed design, which makes them difficult or impossible for patients to remove and insert independently. Consequently, medical practitioners in the United States see most pessary users 3-4 times per year to temporarily remove the pessary, clean it, examine the vagina for epithelial erosions, and then reinsert the pessary.⁶ These steps are needed to avoid preventable complications associated with long term pessary use which have been reported as high as 56%⁷ and include vaginal erosion, bleeding, increased discharge, as well as discomfort

PROTOCOL TITLE: *Early Feasibility Prospective Open Label Study to Assess the Function of a Novel Pessary for the Non-Surgical Management of Pelvic Organ Prolapse*

and dysfunction in voiding and defecation.⁸ Furthermore, women who experience less severe forms of prolapse and who do not need the support of their pessary outside of strenuous physical activity often must wear their pessary when not necessary, which induces additional lifestyle impacts such as impairing a woman's ability to engage in sexual intercourse.

The two most commonly used pessary types on the market are the ring style and the Gellhorn pessary. The Gellhorn pessary is clinically more effective to reduce the life impact of prolapse symptoms,⁹ and once fit has longer continuation rates than the ring with support (10.5 years vs. 1.8 years).¹⁰ Additionally, the Gellhorn successfully treated 71% of women at 3 months who failed treatment with the ring with support.¹¹ Yet most practitioners, particularly Ob/Gyn physicians who are not additionally specialized in FPMRS, preferentially prescribe the ring with support because it is easier and more intuitive to use. The Reia Vaginal Pessary (study pessary) has been engineered to overcome the liabilities related to difficulty for physicians and patients to remove and reinsert the pessary. The Reia Vaginal Pessary has a structural form similar to the Gellhorn and is hypothesized to be simpler and more intuitive to use than the ring with support.

4.0 Study Endpoints

Туре	Name	Time Frame	Brief Description
Primary	To assess the ability of the study device to be retained during Valsalva compared to the ability of the subject's current pessary to be retained during Valsalva (by measuring the distance from each pessary's leading edge to the hymen)	During treatment	The subject will be asked to Valsalva with their current pessary in place, and the distance from the leading edge of the current pessary to the hymen will be measured in centimeters. After the current pessary is removed and the patient is fit with an appropriate study pessary, the subject will be asked to Valsalva again. The distance from the leading edge of the study pessary to the hymen will be measured in centimeters. In order to assess the ability of the study pessary to function and be retained, the measurements will be compared.
Primary	To assess the ability of the study device to be retained throughout regular activity (by vaginal examination)	During treatment	With the study pessary in place, the subject will be asked to ambulate for 10 minutes and attempt to void. Following these activities, whether the pessary was retained or expelled will be recorded.
Secondary	To assess the shape of the study pessary during expulsion if it is not able to be retained (by vaginal examination)	During treatment	The subject will be asked to Valsalva. If the study device is expelled during Valsalva, whether the study device was expelled fully deployed or whether it prematurely folded to its collapsed state will be recorded.

The primary and secondary endpoints of the study are described in the following table:

Secondary	To assess the orientation of the study pessary stem following regular activity (by vaginal examination)	During treatment	Following ambulation and attempting to void and prior to removing the study pessary, it will be recorded if the study device's stem rotated out of its original inserted position.
Secondary	To assess the discomfort experienced with removal of the subject's current pessary compared to the discomfort experienced with removal of the study pessary (by visual analog scale)	During treatment	To indicate discomfort, the subject will be shown and asked to mark a visual analogue scale (VAS) after removal of her current pessary and before using the study pessary. The VAS will be a 10 centimeter linear continuum in which 0 represents no pain and 10 represents worst pain. After use of the study pessary and upon removal of the study pessary, the subject will be shown and asked to mark another VAS. In order to assess the discomfort experienced during removal of the study pessary, the distance from 0 to the subject's mark will be measured and compared between the two scales.
Secondary	To assess the discomfort experienced with insertion of the subject's current pessary compared to the discomfort experienced with insertion of the study pessary (by VAS)	During treatment	To indicate discomfort, the subject will be shown and asked to mark a VAS after insertion of the study pessary. The VAS will be a 10 centimeter linear continuum in which 0 represents no pain and 10 represents worst pain. After use of the study pessary and upon insertion of the subject's current pessary, the subject will also be shown and asked to mark another VAS. In order to assess the discomfort experienced during insertion of the study pessary, the distance from 0 to the subject's mark will be measured and compared between the two scales.
Secondary	To globally assess the comfort associated with use of the study pessary (by verbal description)	Post treatment	Following insertion of the subject's current pessary, and after the subject is dressed, she will be asked whether the study pessary was more, less, or as comfortable as her current pessary when it was in situ. If she responds it was more or less comfortable, she will be asked to describe why.

Safety endpoints cannot be reasonably assessed in this study because risks to subjects are minimal given the short duration of the study intervention (anticipated to be approximately 30 minutes) and the nature of the planned intervention. Pain will be measured as described in the secondary endpoints above. Unanticipated events will be tracked and followed per established FDA guidelines for monitoring investigations of medical devices (21 CFR §812.46).

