- The study pessary will be removed. The orientation of the study pessary inside the vagina will be noted prior to removal. Discomfort with removal will be recorded by VAS. The study pessary will be washed with anti-bacterial soap and tap water and inserted into a resealable bag along with its original packaging. The used study pessary should be returned to [name] office which is adjacent to the clinic space where the study is being conducted *[research purposes]*.
- The current pessary will be re-inserted, *[would be done anyway]* and pain will be recorded by VAS *[research purposes]*. The subject will give a global impression of study pessary comfort in comparison to current pessary *[research purposes]*.

Data Collected

After the subject provides consent, the subject's medical record will be abstracted for their medical history. The subject may be asked to clarify the medical record. Data to be collected includes:

Medical History

- Age
- BMI (kg/m^2)
 - ∘ <20
 - o 20**-**30
 - o >30
- Previous gynecologic surgeries
 - Hysterectomy
 - Prior prolapse surgery
 - Prior UI surgery

- Other gynecologic surgery
- Previous non-surgical prolapse treatment
 - Pelvic floor exercises
 - Pessary use
- Parity
 - No. of births
 - No. of vaginal births
- Estrogen status
 - Pre-menopausal
 - Post-menopausal
 - o HRT
- Concomitant disorders
 - Urinary Incontinence
 - Fecal Incontinence
 - Other
- Prolapse stage
- POP-Q measurements prior to pessary fitting

Outcomes

- Pessary retention and function
 - Retained, normal position
 - Comes out fully deployed before ambulation
 - Collapses and comes out before ambulation
 - Comes out during ambulation
 - Comes out when on toilet, attempting void
- Rotation during ambulation
- Distance from the leading edge of the pessary to hymen with Valsalva
 - Original pessary
 - Study pessary
- Discomfort with insertion and removal (VAS completed by subject)
 - Original pessary
 - Study pessary
- Difficulty with insertion and removal (5 point scale completed by provider)
 - Original pessary
 - Study pessary
- Global impression of comfort while using pessary (3 point scale completed by subject)
- Global impression of ease of use (5 point scale completed by provider)

See attached data collection forms. Forms will be filled out in ink and stored according to procedures outlined in "17.0 Data Management and Confidentiality."

Transition from Research Participation

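### Comfort in use is rated only once, comparatively and by recall, after the study pessary is out and the current one is back in, so removal and re-insertion may influence the answer

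*Protocol*

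**What the plan says.** Protocol Section 6.0 (Methods) treats comfort at insertion, comfort in use and comfort at removal of the study pessary as separate secondary outcomes.

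Insertion and removal are rated close to the event, for both devices. For the current pessary, the subject is "asked to mark a visual analogue scale (VAS) after removal of her current pessary and before using the study pessary", and later, "upon insertion of the subject's current pessary, the subject will also be shown and asked to mark another VAS". Matching scales cover insertion and removal of the study pessary.

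Comfort in use is handled differently. Section 4.0 fixes the timing: "Following insertion of the subject's current pessary, and after the subject is dressed, she will be asked whether the study pessary was more". Three answers are offered (better, worse or the same), and the comparison is confined to how the devices felt while in place. A probe follows: "If she responds it was more or less comfortable, she will be asked to describe why". Study Procedures in Section 6.0 gives the same order. After the current pessary has been re-inserted and its VAS marked, "The subject will give a global impression of study pessary comfort in comparison to current pessary". Data Collected in Section 6.0 lists this as a single three-point item. Unlike the VAS item, it has no separate entries for the original and study pessaries.

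Section 2.0 states more generally that "data will be collected on the performance and comfort of the subject's current pessary" at the visit. It does not say that this means comfort in situ.

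**The concern.** The question is about how the study pessary felt while worn, but it is put after that experience has ended and after two further manipulations. Section 3.0 says the study pessary was engineered to overcome difficulty with removal and reinsertion, and Section 15.0 says it collapses to a smaller diameter than current devices. Handling is therefore where the two devices are expected to differ, and handling comes immediately before the comfort question.

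If removal of the study pessary was easy and re-insertion of the current one unpleasant, a woman may favour the study pessary even if both felt the same in wear. A difficult removal could work the other way. The subject is also unblinded. Section 2.0 says the results will inform design changes, so the sponsor needs to tell a problem of wear from a problem of handling.

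**Working it through.** No arithmetic applies. The plan states no figure for this endpoint, and the SAP deals only with the refitting rate. The check is to put the visit in order, from Section 6.0 (Study Procedures) and Section 4.0, and mark what the subject rates at each step.

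| Step | Pessary in place | Subject-reported rating |
|---|---|---|
| Exam, then Valsalva | Current | None |
| Current pessary removed | None | VAS, removal |
| Study pessary inserted, Valsalva, refit if expelled | Study | VAS, insertion |
| Dress, walk 10 minutes, void, return | Study | None |
| Orientation noted, study pessary removed | None | VAS, removal |
| Current pessary re-inserted | Current | VAS, insertion |
| Dressed, end of visit | Current | Global comfort, comparative |

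Four things follow.

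1. A woman who is not refitted and keeps the study pessary until its planned removal marks four VAS scales, one for each manipulation. She answers one question on comfort in use. The number of stand-alone in-situ ratings is zero for each device.

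2. For that woman, two manipulations (study-pessary removal, current-pessary re-insertion) and two pain ratings lie between wearing the study pessary and being asked about it.

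3. In the Section 4.0 table, global comfort is the only endpoint with a post-treatment time frame. All the others are assessed during treatment.

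4. The two devices are not in the same position when the question is asked. The current pessary is in place, newly re-inserted, and the subject has prior experience of it. The study pessary is remembered from a wear of less than one hour (Section 6.0), within an intervention expected to last about 30 minutes (Section 4.0).

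The existing safeguards were then checked against this sequence. The in-situ wording directs the subject to wear rather than handling, but it does not change the order of events. The free-text reason may show that she was thinking of removal or insertion, but it is not sought from women who answer that the two were equally comfortable. The VAS scores can be set against the global answer. An association would be hard to read, however, because a pessary that fits badly could be uncomfortable both in wear and in handling. Each safeguard helps in part, and none replaces a rating taken while the device is worn.

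**The case against.** The strongest reply is that a direct comparison made after experiencing both devices is a legitimate method, and this one is fenced reasonably well. The question is confined to comfort in situ, handling pain has its own scales, a reason is sought, and recall spans only part of a visit of about one hour. The endpoint is secondary, and the SAP plans no test of it. All of that stands. It is why the existing question should be kept and why this is an inexpensive improvement rather than a flaw that undermines the study.

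Three stronger readings are tempting, and the documents do not support them.

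- A reader might infer from Section 2.0 that promised comfort data on the current pessary are never collected. Section 2.0 does not specify in-situ comfort. The current pessary receives removal and insertion VAS scores and is the comparator in the global question. Only a stand-alone in-situ rating is absent.
- A reader might infer that handling pain does carry over into the answer, in every woman, and cannot be examined afterwards. Nothing in the documents shows that carry-over occurs. Women who expel the study pessary may have no ordinary removal before the question. The VAS scores and free-text reasons allow a partial check.
- A reader might infer that the endpoint should be replaced by a within-woman difference between two contemporaneous ratings. That is a debatable trade. Women who expel the device before the second rating would have no difference score, so missing data would be tied to device failure, and length of wear would still be unequal.

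The attached data collection forms were not available, so an additional comfort item on them cannot be excluded. The list under Data Collected shows none.

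**Conclusion.** The point holds as a limited one. The protocol separates comfort in use from comfort at insertion and removal, rates the latter two as they happen, and leaves the first to a single comparative recall after both pessary changes. The answer may be influenced by those changes, and the present safeguards reduce that possibility without removing it.

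The sequence applies to every woman who keeps the study pessary until its planned removal, out of the 15 in most of the protocol (15 to 20 in the Study Summary). The size of any shift cannot be derived from the documents, and its direction could differ between women. The conclusion assumes that the unseen forms add no in-situ item. It does not mean that the endpoint is without value.

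**What to change.** Add one short comfort-in-use item, worded identically, at two points that the visit already provides:

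1. About the current pessary, on arrival, after consent and before the exam.
2. About the study pessary, after the walk and void and before it is removed. If it was expelled earlier, record that as the reason the rating is missing.

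Report both ratings descriptively, woman by woman, beside the end-of-visit comparative question and its free-text reason, and leave that question in place. Settle the response format at the same time. For global comfort the Study Summary names a VAS, Section 4.0 a verbal description, and Section 6.0 a three-point scale.

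The cost is two lines on the form, a small protocol edit and an estimated one minute of extra questioning per visit. Women who expel the device early will have no rating at the second point. The second rating will still follow insertion and Valsalva, and the unequal length of wear between the two devices remains.

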5.0 Study Intervention/Investigational Agent

Please see attached document for device description and non-significant risk rationale.

6.0 **Procedures Involved**

Methods

Current users of existing marketed pessaries typically present to their providers every 3-4 months so that their pessary can be removed and cleaned and their vagina can be inspected for erosion caused by their device. Fifteen subjects will be recruited for this study from a panel of established patients who present for this routine care of their ring style or Gellhorn pessary to a clinical practice at the Dartmouth-Hitchcock Clinic specializing in Female Pelvic Medicine and Reconstructive Surgery (FPMRS). Inclusion will be based on pre-defined criteria outlined in "10.0 Inclusion and Exclusion Criteria." There will not be discrimination based on race or ethnicity. It is anticipated that most participants will be post-menopausal as this reflects the demographic of women who suffer from this disorder. Treatment intervention will be non-blinded to the subject and investigator and will occur in a single visit. Each subject will receive the study pessary and wear it in a controlled environment for less than 1 hour. Assessment of the study pessary's performance to support the subject's prolapse will be determined by measuring the baseline distance between the leading edge of each subject's current pessary to the hymen and comparing that to the measured distance between the leading edge of the study pessary to the hymen, as well as by observing the ability of the study pessary to be retained with simulated activities of daily life such as walking and toileting. Secondary outcomes of subject comfort with insertion, use, and removal of the study pessary will be measured.

The study pessary is the only device which will be used in this trial, though the subject will arrive for her visit and leave with her current pessary. There will be no placebo devices placed. The study pessary is not cleared by the FDA, and a rationale is provided for a non-significant risk device claim in the attached documents. This trial was devised so that it could take place at the time in which subjects present for usual care of their current pessary, and the procedures are consistent with the standard of care at Dartmouth-Hitchcock Medical Center, the site of the study.

Study Procedures

